#### **8.2.4.1. Tuberculosis Testing**

Participants will be tested as indicated in the SoA (Section 1.3) for evidence of active or latent TB using the QuantiFERON-TB Gold test. If the test is indeterminate, 1 retest is allowed. If the retest is indeterminate, the participant will be excluded from the study.

Participants who have had household contact with a person with active TB must be excluded, unless appropriate and documented prophylaxis treatment for TB has been completed.

Participants with any history of active TB are excluded from the study, regardless of previous or current TB treatments.

#### **8.2.5. Other Tests**

##### **8.2.5.1. Injection-Site Reactions**

Although there will be no prospective collection of ISR information, spontaneously reported ISRs by the participant will be recorded as AEs, with the ISR CRF used to collect supplemental data on the following specific findings:

- induration,
- pain,
- edema,
- pruritus, and
- erythema.

The findings of ISR for a specific injection will be captured as a single AE of injection-site reaction, if 1 or more than 1 of the findings is positive, and the severity that is recorded on the ISR AE form will be the highest severity across the findings at each applicable visit.

If injection-site pain is reported at any time during the study, the intensity of pain will be quantified using the 100-mm validated pain visual analog scale (VAS). The VAS is a well-validated tool (Williamson and Hoggart 2005) to assess injection-site pain; it is presented as a 100-mm line anchored by verbal descriptors, usually “no pain” and “worst imaginable pain.” The participant will be asked to rate any pain at the injection site on a scale of 0 to 100 on the line as soon as is practical following reporting of the event.

Injection-site assessments should be conducted at the next planned visit following the reporting of an injection-related AE.

##### **8.2.5.2. Bleeding/Bruising Assessment**

The presence of visible bleeding/bruising at the injection site will be recorded on the eCRF as applicable and will be recorded as an AE if judged to be more severe than expected with a typical SC administration.

A bandage may be placed on the injection site after assessment.

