### **2.3. Benefit/Risk Assessment**

As with other immunomodulatory therapies, mirikizumab may increase the risk of developing an infection or may exacerbate an existing infection. These may include opportunistic infections and reactivation of latent infections, such as tuberculosis (TB) and hepatitis B, although such infections have not been reported in healthy volunteer clinical trials administering mirikizumab to date. Therefore, participants testing positive for hepatitis B/C, human immunodeficiency virus (HIV), or TB at screening will not be permitted to participate in this study. Immunomodulatory therapies may increase the risk of malignancies; however, due to the single dose of mirikizumab being administered in this study, it is not considered necessary to monitor for such effects.

Immediate hypersensitivity reactions (anaphylactic reaction and infusion-related hypersensitivity reaction) including urticaria, angioedema, and anaphylaxis, have rarely been reported with the administration of mirikizumab.

No other clinically significant safety or tolerability concerns have been identified to date in participants exposed to mirikizumab up to the highest doses given (single 2400-mg IV and SC doses). Of note, the 2400-mg SC dose of mirikizumab was administered in conjunction with human recombinant hyaluronidase as an integral component of the formulation.

Healthy participants are not expected to derive any benefit from participating in studies in which mirikizumab is administered.

As this study will use PFS and AIs, device-based risks will be evaluated. Possible device-based risks include local effects such as pain at the injection sites from either the needle or the solution entry into the SC tissue, swelling, erythema, bleeding, and bruising. These risks are mitigated by training of investigative site staff on proper injection techniques. Systemic effects may include sweating, feeling faint, or fever, as a sign of infection.

More detailed information about the known and expected benefits and risks and reasonably expected AEs of mirikizumab may be found in the IB and risks as well as reasonably anticipated adverse device effects of the AI are found in the device IB.

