## **9. STATISTICAL METHODOLOGY**

### **9.1 General**

Data listings will be provided for all data that is databased. Summary statistics and statistical analysis will only be presented for data where detailed in this SAP. For continuous data, summary statistics will include the arithmetic mean, arithmetic standard deviation (SD), median, minimum, maximum and N; for log-normal data (e.g. the PK parameters: AUCs and  $C_{max}$ ) the geometric mean and geometric CV% will also be presented. For categorical data, frequency count and percentages will be presented. Data listings will be provided for all participants up to the point of withdrawal, with any participants excluded from the relevant population highlighted. Summary statistics and statistical analyses will generally only be performed for participants included in the relevant analysis population. For the calculation of summary statistics and statistical analysis, unrounded data will be used.

Mean change from baseline is the mean of all individual participants' change from baseline values. Each individual change from baseline will be calculated by subtracting the individual participant's baseline value from the value at the timepoint. The individual participant's change from baseline values will be used to calculate the mean change from baseline using a SAS procedure such as Proc Univariate.

Data analysis will be performed using SAS® Version 9.4 or greater.

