## **9.4 Safety and Tolerability Assessments**

### **9.4.1 Adverse events**

Where changes in severity are recorded in the case report form, each separate severity of the AE will be reported in the listings, only the most severe will be used in the summary tables. A pre-existing condition is defined as an AE that starts before the participant has provided written informed consent and is ongoing at consent. A non-treatment emergent AE is defined as an AE which starts after informed consent but prior to dosing. A treatment-emergent AE is defined as an AE which occurs postdose or which is present prior to dosing and becomes more severe postdose.

An adverse device effect (ADE) is defined as an AE related to the use of an investigational medical device. A serious adverse device effect (SADE) is defined as an adverse device effect (ADE) that has resulted in any of the consequences characteristic of an SAE. An unanticipated ADE (UADE) is a SADE which by its nature, incidence, severity, or outcome has not been identified in the current version of the Lilly risk analysis report.

All AEs will be listed. Treatment-emergent AEs will be summarized by treatment, severity and relationship to the study drug. The frequency (the number of AEs, the number of participants experiencing an AE and the percentage of participants experiencing an AE) of treatment-emergent AEs will be summarized by treatment, Medical Dictionary for Regulatory Activities (MedDRA) version 23.0 (or higher if upversioned during the study) system organ class and preferred term. The summary and frequency AE tables will be presented for all causalities and those considered related to the study drug by the investigator. All SAEs, SADEs, and UADEs will be listed.

Discontinuations due to AEs will be listed.

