#### **9.4.10 Injection-Site Reactions**

Although there will be no prospective collection of injection-site reaction (ISR) information, any spontaneously reported ISR by the participant will be reported as AEs.

Any ISR data (including erythema, induration, pain, pruritus, and edema) will be summarized by treatment, and listed.

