#### **9.4.12 Bleeding/Bruising Assessment**

The presence of visible bleeding/bruising at the injection site will be recorded as an AE if judged to be more severe than expected with a typical SC administration.

If available, any bruising or bleeding data will be listed.

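### Bleeding and bruising are counted by treatment only when judged worse than usual; the record of any visible event is listed but not tabulated by device

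*Protocol*

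**What the plan says.** Protocol 2.3 commits to looking at the devices: "As this study will use PFS and AIs, device-based risks will be evaluated". Bleeding and bruising are among the local effects it then names.

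Protocol 8.2.5.2 sets up two tiers of record. The wider one has no severity threshold: "The presence of visible bleeding/bruising at the injection site will be recorded on the eCRF as applicable". The narrower one is the AE record: bleeding or bruising "will be recorded as an AE if judged to be more severe than expected with a typical SC administration". No criterion is given for what counts as expected. The Schedule of Activities has no row or time point for the assessment.

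SAP 9.4.12 repeats the AE rule and adds only this: "If available, any bruising or bleeding data will be listed". SAP 9.1 closes off other summaries: "Summary statistics and statistical analysis will only be presented for data where detailed in this SAP". The AE tier does reach a table, because SAP 9.4.1 states: "Treatment-emergent AEs will be summarized by treatment, severity and relationship to the study drug". For the other local findings, SAP 9.4.10 says: "Any ISR data (including erythema, induration, pain, pruritus, and edema) will be summarized by treatment, and listed".

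The study is open-label (Protocol 6.3), trained site staff give the injections (footnote to Table AMBW.1), and the investigator and designees detect and record AEs (Protocol 8.3).

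**The concern.** The study exists to bridge the manual syringe to the autoinjector, so a reader of the report will want to know whether local device effects differ. For bleeding and bruising, the only count by treatment consists of events that someone who can know the device has judged worse than usual. If that judgement is applied differently to an autoinjector and a syringe, the AE table can show a difference that is not there. If few events pass the judgement in either group, the table can miss a difference that is there. The record that needs no severity judgement has a place on the eCRF, but it has no set time, no guaranteed completion and no table.

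What is at stake is the safety description of one named device risk. The PK comparison and the bioequivalence decision do not depend on it.

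**Working it through.** **Tracing the text.** Each link was checked against the sections cited above.

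1. Bleeding and bruising are named device risks (Protocol 2.3).
2. Any visible event may be entered on the eCRF; only one judged worse than usual becomes an AE (Protocol 8.2.5.2).
3. The eCRF record is listed (SAP 9.4.12), and no summary is presented unless the SAP details it (SAP 9.1).
4. AEs are summarised by treatment (SAP 9.4.1), so the only planned count by treatment has passed through the judgement.
5. The injection-site reaction summary does not fill the gap. The supplemental form in Protocol 8.2.5.1 covers induration, pain, edema, pruritus and erythema; bleeding and bruising have their own section.
6. Protocol 8.2.5.2 does not say who judges. Site staff are an inference from the open-label design and from who doses and records AEs.

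**Figures.** The documents state no figure for bleeding or bruising, so there is none to reproduce. The one design figure, about 90% power for the PK comparison, has no bearing here. The only document input below is the target of 108 completers per device (Protocol 9.2). The rates are assumptions.

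Let v be the proportion with visible bleeding/bruising and q the share of those events judged worse than usual. The expected AE count per group is 108 × v × q. If v is equal in both groups, the AI:PFS ratio in the AE table is q(AI)/q(PFS), whatever v is.

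| v, both groups | q PFS | q AI | AEs PFS | AEs AI | Ratio shown |
|---|---|---|---|---|---|
| 10% | 20% | 20% | 2.16 | 2.16 | 1.0 |
| 10% | 20% | 10% | 2.16 | 1.08 | 0.5 |
| 10% | 20% | 30% | 2.16 | 3.24 | 1.5 |
| 10% | 10% | 30% | 1.08 | 3.24 | 3.0 |
| 20% | 20% | 20% | 4.32 | 4.32 | 1.0 |
| 20% | 20% | 10% | 4.32 | 2.16 | 0.5 |
| 20% | 20% | 30% | 4.32 | 6.48 | 1.5 |
| 20% | 10% | 30% | 2.16 | 6.48 | 3.0 |
| 30% | 20% | 20% | 6.48 | 6.48 | 1.0 |
| 30% | 20% | 10% | 6.48 | 3.24 | 0.5 |
| 30% | 20% | 30% | 6.48 | 9.72 | 1.5 |
| 30% | 10% | 30% | 3.24 | 9.72 | 3.0 |

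The true ratio is 1.0 in every row. The 20% row with q of 10% versus 30% is 0.20 × 0.10 = 2% against 0.20 × 0.30 = 6%. Swapping the q values between devices reverses the direction.

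**The opposite case, a real difference hidden.** Assume v = 10% versus 25% and q = 10% in both groups. The AE table expects 108 × 0.10 × 0.10 = 1.08 against 108 × 0.25 × 0.10 = 2.70 events. A complete record of visible events would expect 10.8 against 27:

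- difference = 0.25 − 0.10 = 15 points
- SE = √[(0.10 × 0.90 + 0.25 × 0.75)/108] = √(0.2775/108) = 0.0507
- 95% CI = 15 ± 1.96 × 5.07 = 5.1 to 24.9 points

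That interval assumes every participant is assessed and capture is equal between devices, which the present eCRF wording does not secure.

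**The case against.** The strongest reply is that the plan never promised a between-device comparison of bleeding. The secondary objective is to describe safety and tolerability. The commitment in Protocol 2.3 sits in a benefit/risk narrative, and device risk is also followed through adverse device effects, device deficiencies and product complaints. This stands: nothing here asks for a formal test. A description of a named risk is still easier to use with a count by device than with a listing that readers must tally themselves.

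A reader might also infer that the eCRF record is unfiltered, so that tabulating it would give an unbiased comparison. The documents do not support that. The record has no severity threshold, but it is filled in as applicable, listed if available, and made in the same open-label setting. A blank could mean absent or not assessed. Tabulated as now collected, it would have no sound denominator.

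Nor do the documents show that staff apply different thresholds. The benchmark is worded the same for both devices. Differential judgement is a possibility that the design leaves open, not a finding.

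The contrast with the injection-site reaction findings has limits too. Those rest on spontaneous reports, and every reported reaction is an AE, which gives some logic to the different handling.

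Finally, the plan leaves room for a summary. Protocol 9.4.3.1 allows safety data to be summarised if frequency permits, and SAP section 3 allows supplementary analyses identified in the CSR. But SAP section 3 also says that the SAP supersedes the protocol's statistical considerations, and SAP 9.4.12 specifies a listing. The route is discretionary and softens the gap without closing it.

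**Conclusion.** The point holds in a narrow form. A named device risk is counted by treatment only after an open-label judgement with no stated criterion, while the wider record has no defined time and no summary. The AE table alone therefore cannot tell a device difference from a threshold difference.

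No size can be taken from the documents. Under the assumed pass rates, the AE table would show AI:PFS ratios from 0.5 to 3.0 where the true ratio is 1.0. These are illustrations only; the bias is possible, not demonstrated, and could go either way.

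It would be wrong to read this as a flaw in the bioequivalence conclusion or as a broken commitment to test the devices against each other. It is a low-cost improvement to a descriptive safety output.

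**What to change.** **eCRF completion.** Instruct sites to complete the existing bleeding/bruising item as yes or no for each injection, in every dosed participant, on Day 1 before discharge. Protocol 8.2.5.2 already presumes a look at the site, since it mentions a bandage after assessment; the Schedule of Activities should give that look a time point. The instruction must be in place before dosing, because an absence that was not recorded cannot be recovered later.

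**SAP 9.4.12.** Add one descriptive table of any visible bleeding/bruising, AI versus PFS, pooled over injection sites and also by site. Use all dosed participants as the denominator and state the time point. Pooling by device needs to be spelled out because SAP section 6 defines the table treatments as six device-by-site groups. Keep the listing, including events reported later, and keep the AE table.

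**Cost.** One table, a short completion instruction and a Schedule of Activities entry; no extra visit. The entry makes explicit a site check that the schedule does not now list.

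**What remains.** The yes/no record is still made unblinded, and a Day 1 record will miss bruising that appears later. The change lessens the dependence on a severity threshold; it does not remove bias.

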### 8.2.6. Safety Monitoring

The Lilly CP or clinical research physician/scientist will monitor safety data throughout the course of the study.

Lilly will review SAEs within time frames mandated by company procedures. The Lilly CP or CRP will periodically review

- trends in safety data
- laboratory analytes, and
- AEs.

When appropriate, the Lilly CP or CRP will consult with the functionally independent Global Patient Safety medical physician or clinical research scientist.

#### 8.2.6.1. Hepatic Safety

##### Close hepatic monitoring

Laboratory tests (Appendix 6, Section 10.6), including alanine aminotransferase (ALT), aspartate aminotransferase (AST), alkaline phosphatase (ALP), total bilirubin (TBL), and direct bilirubin, should be repeated within 48 to 72 hours if possible with additional testing for gamma-glutamyltransferase and creatine kinase, to confirm the abnormality and to determine if it is increasing or decreasing, if 1 or more of these conditions occur:

If a participant with baseline results of ...	develops the following elevations:
ALT or AST $<1.5 \times$ ULN	ALT or AST $\geq 3 \times$ ULN
ALP $<1.5 \times$ ULN	ALP $\geq 2 \times$ ULN
TBL $<1.5 \times$ ULN	TBL $\geq 2 \times$ ULN (except for participants with Gilbert's syndrome)
ALT or AST $\geq 1.5 \times$ ULN	ALT or AST $\geq 2 \times$ baseline
ALP $\geq 1.5 \times$ ULN	ALP $\geq 2 \times$ baseline
TBL $\geq 1.5 \times$ ULN	TBL $\geq 2 \times$ baseline (except for participants with Gilbert's syndrome)

If the abnormality persists or worsens, clinical and laboratory monitoring, and evaluation for possible causes of abnormal liver tests should be initiated by the investigator in consultation with the Lilly-designated CP. At a minimum, this evaluation should include physical examination and a thorough medical history, including symptoms, recent illnesses (for example, heart failure, systemic infection, hypotension, or seizures), recent travel, history of concomitant medications (including over-the-counter), herbal and dietary supplements, history of alcohol drinking and other substance abuse.

Initially, monitoring of symptoms and hepatic biochemical tests should be done at a frequency of 1 to 3 times weekly, based on the participant's clinical condition and hepatic biochemical tests.

Subsequently, the frequency of monitoring may be lowered to once every 1 to 2 weeks, if the participant's clinical condition and lab results stabilize. Monitoring of ALT, AST, ALP, and TBL should continue until levels normalize or return to approximate baseline levels.

**Comprehensive hepatic evaluation**

A comprehensive evaluation should be performed to search for possible causes of liver injury if 1 or more of these conditions occur:

If a participant with baseline results of...	develops the following elevations:
ALT or AST <1.5× ULN	ALT or AST $\geq 3 \times$ ULN with hepatic signs/symptoms*, or ALT or AST $\geq 5 \times$ ULN
ALP <1.5× ULN	ALP $\geq 3 \times$ ULN
TBL <1.5× ULN	TBL $\geq 2 \times$ ULN (except for participants with Gilbert's syndrome)
ALT or AST $\geq 1.5 \times$ ULN	ALT or AST $\geq 2 \times$ baseline with hepatic signs/symptoms*, or ALT or AST $\geq 3 \times$ baseline
ALP $\geq 1.5 \times$ ULN	ALP $\geq 2 \times$ baseline
TBL $\geq 1.5 \times$ ULN	TBL $\geq 1.5 \times$ baseline (except for participants with Gilbert's syndrome)

\* Hepatic signs/symptoms are severe fatigue, nausea, vomiting, right upper quadrant abdominal pain, fever, rash, and/or eosinophilia >5%.

At a minimum, this evaluation should include physical examination and a thorough medical history, as outlined above, as well as tests for prothrombin time - international normalized ratio (PT-INR); tests for viral hepatitis A, B, C, or E; tests for autoimmune hepatitis; and an abdominal imaging study (for example, ultrasound or computerized tomography [CT] scan).

Based on the participant's history and initial results, further testing should be considered in consultation with the Lilly-designated CP, including tests for hepatitis D virus (HDV), cytomegalovirus (CMV), Epstein-Barr virus (EBV), acetaminophen levels, acetaminophen protein adducts, urine toxicology screen, Wilson's disease, blood alcohol levels, urinary ethyl glucuronide, and serum phosphatidylethanol. Based on the circumstances and the investigator's assessment of the participant's clinical condition, the investigator should consider referring the participant for a hepatologist or gastroenterologist consultation, magnetic resonance cholangiopancreatography (MRCP), endoscopic retrograde cholangiopancreatography (ERCP), cardiac echocardiogram, or a liver biopsy.

**Additional hepatic data collection (hepatic safety eCRF) in study participants who have abnormal liver tests during the study**

Additional hepatic safety data collection in the hepatic safety eCRF should be performed in study participants who meet 1 or more of the following 5 conditions:

1. Elevation of serum ALT to  $\geq 5 \times$  ULN on 2 or more consecutive blood tests (if baseline ALT  $< 1.5 \times$  ULN)
  - In participants with baseline ALT  $\geq 1.5 \times$  ULN, the threshold is ALT  $\geq 3 \times$  baseline on 2 or more consecutive tests
2. Elevated TBL to  $\geq 2 \times$  ULN (if baseline TBL  $< 1.5 \times$  ULN) (except for cases of known Gilbert's syndrome)
  - In participants with baseline TBL  $\geq 1.5 \times$  ULN, the threshold should be TBL  $\geq 2 \times$  baseline
3. Elevation of serum ALP to  $\geq 2 \times$  ULN on 2 or more consecutive blood tests (if baseline ALP  $< 1.5 \times$  ULN)
  - In participants with baseline ALP  $\geq 1.5 \times$  ULN, the threshold is ALP  $\geq 2 \times$  baseline on 2 or more consecutive blood tests
4. Hepatic event considered to be an SAE
5. Discontinuation of study drug due to a hepatic event

Note: The interval between the 2 consecutive blood tests should be at least 2 days.

### **8.3. Adverse Events and Serious Adverse Events**

The definitions of device-related safety events, (adverse device effects [ADEs], unanticipated adverse device effects [UADEs], and serious adverse device effects [SADEs]), can be found in Appendix 8 (Section 10.8). Product complaints are covered in Section 8.3.7.

Adverse events will be reported by the participant (or, when appropriate, by a caregiver, surrogate, or the participant's legally authorized representative).

The investigator and any qualified designees are responsible for detecting, documenting, and recording events that meet the definition of an AE or SAE and remain responsible for following up AEs that are serious, considered related to the study intervention or study procedures, or that caused the participant to discontinue the study (see Section 7).

Investigators are responsible for monitoring the safety of participants who have entered this study and for alerting Lilly or its designee to any event that seems unusual, even if this event may be considered an unanticipated benefit to the participant.

The investigator is responsible for the appropriate medical care of participants during the study.

